10 OUTCOME MEASURES

The following outcome measures will be assessed at 6 months and 12 months and compared to published and/or retrospective data for autograft or other similar products:

Study objectives are to detect:

- Fusion rates as determined by radiographic imaging at 6 and 12 months post-surgery.
 - Fusion of the interbody space shall be deemed successful if the following radiographic endpoints are demonstrated on x-ray examination (lateral, anterior/posterior, flexion and extension): Evidence of bridging trabecular bone between the involved motion segments, translational motion <3mm; and angular motion <5°.¹
- Changes in Oswestry Disability Index/Neck Disability Index from baseline, at all available follow-up time-points.
- Changes in Visual Analog Scale (VAS) from baseline, at all available follow-up time-points.

Safety evaluations include:

- Incidence of ViBone-related serious adverse reactions.

	DOCUMENT TITLE: A Prospective, Post-Market, Multi-Center Study Evaluating ViBone in Cervical and Lumbar Spine Fusion	DOCUMENT NUMBER: CLP-0001
--	---	-------------------------------------

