DOCUMENT TITLE: A Prospective, Post-Market, Multi-Center Study Evaluating ViBone in Cervical and Lumbar Spine Fusion	DOCUMENT NUMBER: CLP-0001
--	---	-------------------------------------

A Prospective, Post-Market, Multi-Center Study Evaluating ViBone® in Cervical and Lumbar Spine Fusion

Clinicaltrials.gov Identifier:

NCT03425682

Original Protocol Version Date: 11/17/2017

Sponsor:
Aziyo Biologics, Inc.
Corporate Headquarters
[name]
[name] 20904

Sponsor contact:
[name]
[contact]
[contact]

	DOCUMENT TITLE: A Prospective, Post-Market, Multi-Center Study Evaluating ViBone in Cervical and Lumbar Spine Fusion	DOCUMENT NUMBER: CLP-0001
--	---	-------------------------------------

Protocol Synopsis

Company:	Aziyo Biologics, Inc.
Protocol Number:	CLP-0001
Product:	ViBone® Viable Bone Matrix
Protocol Title:	A Prospective, Post-Market, Multi-Center Study Evaluating ViBone in Cervical and Lumbar Spine Fusion
Treatment Indication:	Spondylosis, spondylolisthesis, degenerative disc disease, or herniated nucleus pulposus affecting either 1 to 3 contiguous levels between C2 and C7 (for cervical patients) or L1 and S1 (for lumbar patients).
Purpose:	
The purpose of this study is to assess clinical and radiographic outcomes in patients who undergo 1-3 level anterior cervical discectomy fusion (ACDF) or lumbar interbody fusion (TLIF, PLIF, ALIF, LLIF) using ViBone. Subjects will be followed for 12 months following surgery to determine the number of study subjects that are solidly fused at or before 12 months postoperatively.
 
The data for cervical and lumbar fusions will be analyzed separately and will be compared to published and/or retrospective data for autograft or other similar graft materials.

Design:	
Up to 50 patients undergoing ACDF using ViBone will be enrolled.
 
Up to 50 patients undergoing lumbar interbody fusion using ViBone will also be enrolled.
 
Subjects will be followed via the enrolling center's standard of care for the procedure.
 
Data from patients meeting the study criteria will be gathered at baseline, 6 months, and 12 months post-surgery.

	DOCUMENT TITLE: A Prospective, Post-Market, Multi-Center Study Evaluating ViBone in Cervical and Lumbar Spine Fusion	DOCUMENT NUMBER: CLP-0001
--	--	-------------------------------------

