6 PATIENT SELECTION

6.1 Study Population

Up to 50 ACDF and up to 50 lumbar interbody fusion patients from up to twenty centers in the United States will be enrolled. The study population will consist of male and female patients, 18-80 years of age. Eligible patients should have spondylosis, spondylolisthesis, degenerative disc disease, or herniated nucleus pulposus. Cervical fusion patients shall undergo ACDF surgery using ViBone at 1 to 3 contiguous levels between C2 and C7. Lumbar fusion patients shall undergo lumbar interbody fusion surgery using ViBone at 1 to 3 contiguous levels between L1 and S1.

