6.2 Eligibility criteria

6.2.1 Informed Consent Form

Each patient will be required to sign an IRB-approved ICF prior to enrollment in the study.

The ICF and product package insert will be used to explain the study and fully disclose known risks and benefits. Subjects will not directly benefit from being in this study; however, the results of this study may help people undergoing spine fusion in the future. As with implantation of all human allograft tissue, risks associated with the implantation of ViBone include lack of response from the recipient (e.g., lack of fusion or non-union with adjacent tissue). It is also possible for a host site to become infected or the allograft tissue may cause an inflammatory response. Current technologies may not preclude the transmission of infectious agents or disease, including hepatitis and HIV. ViBone is preserved in 5% dimethyl sulfoxide (DMSO) in a 0.9% sodium chloride solution. Povidone iodine, Dulbecco's phosphate buffered saline, sodium chloride irrigation solution, sodium phosphate, hydrochloric acid and hydrogen peroxide are all used for processing, preservation and storage of the allografts and trace amounts of these solutions may be present in the product.

There are no additional medical risks involved in participating in this study. The only additional risk from taking part in this study is that the confidentiality of subject information may be lost or compromised.

The ICF must include the elements required by the FDA in US 21 CFR 50 and International Conference on Harmonization (ICH) guidelines.

Patients will also be required to consent to the use of their PHI according to all applicable health information privacy regulations. This authorization can be part of the ICF or can be a separate document.

Each Investigator participating in the study is responsible for obtaining approval from Aziyo for any consent documents prior to their submission to their IRB and prior to their use. Each Investigator participating in the study is also responsible for ensuring that a written ICF and written authorization for use of PHI are obtained from each patient that they enroll into the study at the time of that patient's enrollment. Documentation of the informed consent process must be completed by research personnel and the patient will receive a copy of the signed ICF. No study-related activities may be performed on any patient and no data may be

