7.2.3 Follow-Up Visits

Study-related Follow-Up Visits shall occur at 6 months and 12 months (\pm 1 month) after the date of the surgical procedure. The following information shall be collected at each Follow-Up Visit:

- Surgical Complication Assessment
- Oswestry Disability Index (lumbar fusion) or Neck Disability Index (cervical fusion)
- Visual Analog Scale (both leg and back pain)
- Radiological Assessment – at minimum, lateral, anterior/posterior, flexion and extension radiographs are required at each follow-up visit. If performed, CT scans will also be collected.

	DOCUMENT TITLE: A Prospective, Post-Market, Multi-Center Study Evaluating ViBone in Cervical and Lumbar Spine Fusion	DOCUMENT NUMBER: CLP-0001
--	--	-------------------------------------

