9 PREMATURE SUBJECT WITHDRAWAL

Participation is voluntary and all subjects have the right to withdraw their participation from the study at any time. Subjects will be withdrawn from the study immediately if any of the following occurs:

- the Investigator determines it is in the best interest of the subject, or
- the subject withdraws informed consent, or
- the subject withdraws authorization to use protected health information.

Aziyo or its designee must be notified promptly when a subject is withdrawn. The Investigator will encourage all subjects who decide to withdraw from the study to complete all evaluations that may be necessary to ensure that the subject is free of untoward effects and to seek appropriate follow-up for any continuing problems. The date the subject is withdrawn from the study and the reason for discontinuation will be recorded in the electronic data capture system. When a subject is withdrawn from the study, regardless of the reason, all evaluations required at the final study visit should be performed.

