12 STATISTICAL CONSIDERATIONS

As this study is designed to assess the clinical and radiographic outcomes in patients who undergo cervical (ACDF) or lumbar (TLIF, PLIF, LLIF, or ALIF) spine fusion surgery using ViBone, statistics will be descriptive. Baseline demographic and clinical variables will be summarized. Frequencies and percentages with confidence intervals will be tabulated for surgical outcomes.

	DOCUMENT TITLE: A Prospective, Post-Market, Multi-Center Study Evaluating ViBone in Cervical and Lumbar Spine Fusion	DOCUMENT NUMBER: CLP-0001
--	---	-------------------------------------

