- The allograft expiration date has passed.
- Recommended storage conditions have not been maintained.

INSTRUCTIONS FOR USE

It is important to utilize aseptic techniques when unpacking the allograft.

1. Examine the labeling and outer peel pouch. Do not use if there is evidence that the integrity of the outer pouch has been compromised.
2. Aseptically present the inner jar onto a sterile field.
3. Place the unopened jar into a sterile basin and fill with warm (approximately 37°C) sterile saline to just below the jar lid.
4. Thaw ViBone™ for approximately 5-15 minutes.
5. Don sterile surgical gloves, remove the jar lid and remove the product from the jar.
6. The allograft tissue should be pliable. If the allograft is still frozen, warm by holding the allograft with sterile gloved hands until completely thawed and pliable.
7. ViBone™ should be transplanted within two hours of thawing and all unused product must be discarded. Product is intended for single use and should not be refrozen or sterilized.

TRACEABILITY

The FDA requires traceability from the donor to the recipient. The physician is responsible for completing the recipient records to ensure traceability. As a convenience, pre-printed peel-off labels are included with each allograft. Using the labels, record the allograft tissue identification information in the patient medical record.

ADVERSE REACTION

The physician must promptly report any adverse outcomes potentially attributable to ViBone™ to Aziyo at [contact].

Manufactured By:

Aziyo Biologics, Inc.
[name]
[name]
[contact]
[contact]

FDA Registration No. 1000100754
CTO Registration Certificate No. 100242
Accredited by the AATB™

American Association of Tissue Banks™ and AATB™ are registered service marks of the American Association of Tissue Banks™.

IFU-0006 Rev 05

	DOCUMENT TITLE: A Prospective, Post-Market, Multi-Center Study Evaluating ViBone in Cervical and Lumbar Spine Fusion	DOCUMENT NUMBER: CLP-0001
--	---	-------------------------------------

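### Section 10 gives no endpoint status for a treated level re-operated on after the index surgery; applied literally, one that is re-grafted and then bridges counts as fused

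*Combined protocol and SAP*

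**What the plan says.** Section 10 defines success for a single level: "Fusion of the interbody space shall be deemed successful if the following radiographic endpoints are demonstrated on x-ray examination". The findings are bridging trabecular bone, translation below 3 mm and angulation below 5°, read on lateral, anterior/posterior, flexion and extension films. Nothing in the definition depends on what has been done to the level since the index operation.

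The Synopsis, by contrast, counts people. Its purpose is to "determine the number of study subjects that are solidly fused at or before 12 months postoperatively". The primary outcome there is fusion by 12 months, whereas Sections 4.2 and 5.1 speak of fusion at 12 months. A subject may contribute several levels. Section 6.1 says "Cervical fusion patients shall undergo ACDF surgery using ViBone at 1 to 3 contiguous levels between C2 and C7", and allows the same number of lumbar levels between L1 and S1. No section says how level results combine into a subject result.

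Four other places could touch a re-operation:
- Section 7.2.3 lists a "Surgical Complication Assessment" at each follow-up visit.
- Section 9 lets the investigator withdraw a subject and has the reason recorded, but adds: "When a subject is withdrawn from the study, regardless of the reason, all evaluations required at the final study visit should be performed".
- The package insert (Appendix 4) says: "The physician must promptly report any adverse outcomes potentially attributable to" ViBone to the manufacturer.
- Section 11.1 requires a Serious Adverse Reaction form for reactions involving a communicable disease.

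On analysis, Section 12 is descriptive: "Frequencies and percentages with confidence intervals will be tabulated for surgical outcomes". Sections 10 and 16.2 plan a comparison with published or retrospective data.

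**The concern.** Failure of the graft is a foreseen event. Section 6.2.1 lists among the risks "lack of response from the recipient (e.g., lack of fusion or non-union with adjacent tissue"). A patient with a non-union may be re-operated on, and the new graft or fixation may then produce bridging. Under the Section 10 wording that level meets the definition, so a failure of the index graft appears in the primary measure as its opposite.

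Because no rule is written, three codings are available for the same level: fused, not fused, or left out. The choice could be made after the films have been read. The external comparison is also hard to interpret if the published or retrospective series count re-operated levels differently, and the plan does not ask whether they do.

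**Working it through.** **Step 1. Does any text settle the status?** The plan states no figure on this point, so there is none to reproduce; the check is of the text. Take a treated level that has not bridged, is re-grafted, and meets the three criteria on the 12-month film.
- Section 10: the criteria are met, so the level is successful.
- Section 7.2.3: the event may be recorded, but the assessment is not linked to fusion status.
- Section 9: re-operation is not named. If the investigator withdraws the subject, final-visit evaluations are still requested, so a film taken after the re-operation can exist with no rule for using it.
- Section 11.1: limited to communicable-disease reactions, so surgery for non-union falls outside it.
- Appendix 4: a reporting duty that sets no endpoint status.
- Section 7.2.2: at least 70% of the graft volume should be ViBone, but this sits under the index surgical visit and says nothing about a later re-graft.
- Section 12: no rule for events after surgery or for missing films.

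Only Section 10 yields an answer, and that answer is success.

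**Step 2. A second case.** A level meets the criteria at 6 months, is then re-grafted for non-union, and bridges again at 12 months. Under the Synopsis wording (at or before 12 months) the 6-month film alone makes it a success. Under Sections 4.2 and 5.1 (at 12 months) the result rests on a film taken after the re-operation. A counting rule that applied only to levels not yet meeting the criteria would miss this case.

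**Step 3. Size per case.** Inputs: up to 50 subjects per cohort (Section 12.1) and 1 to 3 levels each (Section 6.1).
- Per subject, success versus failure coding moves the rate by 1/n: 1/50 = 2.0 points. Enrolment is a maximum, so this is not a ceiling: with 40 evaluable, 1/40 = 2.5 points.
- Per level, 50 subjects give 50 to 150 levels: 1/50 = 2.0, 1/100 = 1.0, 1/150 = 0.67 points.

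**Step 4. Illustration with assumed counts.** The documents give neither a fusion rate nor a re-operation rate. Assume 45 of 50 subjects meet the x-ray criteria and k of those 45 were re-operated on before bridging. The literal rate is then 45/50 = 90.0% for every k, with exact (Clopper-Pearson) 95% interval 78.2–96.7%.

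| k | Counted as not fused: (45−k)/50 | Excluded: (45−k)/(50−k) |
|---|---|---|
| 1 | 44/50 = 88.0% (75.7–95.5) | 44/49 = 89.8% (77.8–96.6) |
| 2 | 43/50 = 86.0% (73.3–94.2) | 43/48 = 89.6% (77.3–96.5) |
| 3 | 42/50 = 84.0% (70.9–92.8) | 42/47 = 89.4% (76.9–96.5) |
| 5 | 40/50 = 80.0% (66.3–90.0) | 40/45 = 88.9% (75.9–96.3) |

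Per level, assuming 150 levels and three such cases: 129/150 = 86.0% (79.4–91.1) if counted as fused, 126/150 = 84.0% (77.1–89.5) if counted as not fused, and 126/147 = 85.7% if excluded. The per-level intervals treat levels within a subject as independent, so they are if anything too narrow.

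Exclusion stays close to the literal rate. The choice that matters is between success and failure.

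**The case against.** The strongest reply is that silence is not a rule. A reader might infer that the protocol deliberately credits a re-grafted level to ViBone. The documents do not support that. The stated purpose is outcomes of fusion surgery using ViBone, follow-up is timed from the surgical procedure, and the 70% floor in Section 7.2.2, though not a rule for re-grafts, weighs against crediting another graft. An analyst could reasonably code failure or exclusion. This objection stands as a limit on the claim: the status is unstated, and the unwanted result follows from applying Section 10 as written.

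A reader might also infer that re-operations go unrecorded. That is not supported either: the complication assessment, the withdrawal reason and the package-insert duty may all record them. The case report forms were not available, and they may already hold level, date and reason.

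A third tempting inference is that the fusion rate is materially inflated. The documents give no re-operation rate, and failure, further surgery and new bridging must all occur before the 12-month film. Cases are likely few. There is no test, margin or target rate, and the intervals in Step 4 overlap.

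What this does not answer is that in a descriptive single-arm study the percentage and its interval are the result. The definition of success therefore decides what is reported and compared.

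**Conclusion.** The gap is real and worth closing before films are read. Section 10 decides fusion on three x-ray findings alone, and nothing else in the available text sets the status of a re-operated level. Followed literally, a failed ViBone level that is re-grafted or re-fixed and then bridges by 12 months counts as a success.

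The effect is 1/n per case: 2.0 points per subject at n = 50 and 2.5 at n = 40, or 0.67 to 2.0 points per level for 50 to 150 levels. How many cases will arise is unknown and probably small. The effect is on the reported rate and its external comparison, not on any hypothesis test.

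This rests on two assumptions. One is that the investigator agreement and sample consent form, which were not available, contain no endpoint rule; they are unlikely places for one. The other is the cohort size. Section 5.1 expects about 200 subjects in total, while the two caps of 50 sum to 100, so n itself needs reconciling.

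**What to change.** This is a counting rule only, with no change to surgical practice. Add to Section 10:
- A treated level that, after the index surgery, has its graft removed, replaced or supplemented, or has fixation added at that level, is counted as not fused at every assessment after that surgery. If the surgery was for suspected or confirmed non-union, it is also not fused in the 12-month primary result, even if an earlier film met the criteria.
- Removal of index hardware alone, with the index graft left in place, does not by itself count as failure.
- For subject-level rates, a subject is fused only if every treated level is fused.

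In the same edit, reconcile fusion by 12 months with fusion at 12 months. That difference decides the primary status of a level that met the criteria at 6 months and was then re-operated on for a reason other than non-union.

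Record level, date and reason of each re-operation in the Surgical Complication Assessment, if not already captured. List the re-operations, report the x-ray-only rate as a sensitivity result, and state whether the comparison data use the same rule or that this is not known.

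The cost is a few sentences in Section 10, at most three data fields, one listing, one extra rate and one sentence on the comparison data. The reported rate may be slightly less favourable. Some re-operations unrelated to the graft will count as not fused; the listed reasons and the x-ray-only rate make that visible. If the comparison series used another rule, the x-ray-only rate is also the fallback for that comparison.

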11 SAFETY

11.1 Reporting Serious Adverse Reactions

Adverse Reactions involving a communicable disease and are deemed related to use of ViBone, will be reported to FDA's MedWatch program and details of the event shall be documented on the applicable Serious Adverse Reaction form.² Per FDA 21 CFR 1271.3 (y), an adverse reaction is defined as a noxious and unintended response to any HCT/P for which there is a reasonable possibility that the HCT/P caused the response.

Per FDA 21 CFR 1271.350 adverse reactions involving a communicable disease related to an HCT/P (ViBone) must be investigated and reported to the FDA within 15 calendar days of initial receipt of the information. Adverse reactions are further defined to include the following:

A communicable disease that:

1. **Is fatal** (report if you suspect the death was an outcome of the adverse event);
2. **Is life threatening** (subject at substantial risk of dying at the time of the adverse event, or use or continued use of the device or other medical product might have resulted in the death of the subject);
3. **Results in permanent impairment of body function or permanent damage to body structure** (Report if the adverse event resulted in a substantial disruption of a person's ability to conduct normal life functions, i.e., the adverse event resulted in a significant, persistent or permanent change, impairment, damage or disruption in the subject's body function/structure, physical activities and/or quality of life); or
4. **Necessitates medical or surgical intervention, including hospitalization** (report if hospitalization is the result of an adverse event. Emergency department visits that do not result in admission should be evaluated for one of the other outcomes).

If an adverse reaction involving a communicable disease that is believed to be related to the use of ViBone occurs, a Serious Adverse Reaction form shall be completed. In addition to completing the form, Aziyo must be notified within 24 hours of the Investigator becoming aware of the event. All fields are required in order to provide Aziyo personnel with the required information to evaluate the reaction and complete the required MedWatch report for submission to FDA per the Sponsor's Medical Device Reporting SOP.

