Patient Population:	
Included are both male and female patients, 18-80 years of age with spondylosis, spondylolisthesis, degenerative disc disease, or herniated nucleus pulposus affecting 1, 2, or 3 contiguous levels of the spine between C2 and C7 (for cervical patients) or L1 and S1 (for lumbar patients).
 
Patients must be undergoing ACDF or lumbar interbody fusion using ViBone to be eligible for the study.

Outcome Measures:	
Primary:
 
 Incidence of successful fusion measured radiographically by 12 months post-surgery 
Secondary:
 
 Incidence of successful fusion measured radiographically by 6 months post-surgery Oswestry Disability Index (ODI)/Neck Disability Index (NDI) relative to baseline. Visual Analog Scale (VAS) relative to baseline. Incidence of subjects experiencing ViBone-related serious adverse reactions.
Duration:	Subjects will be evaluated via routine follow up visits through 12 months post-surgery.
Centers:	Up to 20 centers in the U.S.

	DOCUMENT TITLE: A Prospective, Post-Market, Multi-Center Study Evaluating ViBone in Cervical and Lumbar Spine Fusion	DOCUMENT NUMBER: CLP-0001
--	---	-------------------------------------

Study contact for discussion of protocol-specific issues:

[name]

Aziyo Biologics, Inc.

[contact]

Email: [contact]

**SAFETY REPORTING CONTACT INFORMATION:
REPORTING OF SAFETY INFORMATION TO SPONSOR**

Aziyo pharmacovigilance designee and contact information for adverse reaction reporting:

[name]

Aziyo Biologics, Inc.

[contact]

Email: [contact]

Table of Contents

1	ABBREVIATIONS	7
2	TRADEMARK STATEMENTS	8
3	INTRODUCTION	8
3.1	Spine Fusion	8
3.2	Viable Bone Allografts	8
3.3	Description of ViBone	8
4	STUDY PURPOSE AND OBJECTIVES	9
4.1	Study Purpose	9
4.2	Objectives	9
5	STUDY DESIGN	9
5.1	Design Summary	9
5.2	Patient Enrollment	9
6	PATIENT SELECTION	10
6.1	Study Population	10
6.2	Eligibility criteria	10
6.2.1	Informed Consent Form	10
6.2.2	Inclusion Criteria	11
6.2.3	Exclusion Criteria	11
7	STUDY PROCEDURES	12
7.1	Schedule of Assessments	12
7.2	Study Visits	13
7.2.1	Pre-Surgery Screening Visit	13
7.2.2	Surgical Procedure Visit	13
7.2.3	Follow-Up Visits	13
7.2.4	Subject Close-Out	14

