7 STUDY PROCEDURES

7.1 Schedule of Assessments

Study assessments are summarized below in Table 1, and are further described in Section 7.2.

Table 1: Schedule of Assessments

	Pre-Surgery Screening Visit	Surgical Procedure Visit	Follow-Up Visits (+/- 1 Month)
Visit Window	Day -30 to 0	Day 0	6 and 12 Months Post Surgery
Inclusion/Exclusion Determination	X		
Informed Consent/PHI Authorization	X		
Baseline Demographics and Basic Patient Information	X		
Surgical Procedure Details		X	
Radiological Assessment (including flexion/extension)	X ^{1,2}		X ³
Oswestry Disability Index (Lumbar Fusion) or Neck Disability Index (Cervical Fusion)	X		X
Visual Analog Scale (Both Leg and Back Pain)	X		X
ViBone-Related Serious Adverse Reactions Assessment			As needed

¹ Baseline radiographs may be up to 12 months prior to the surgical procedure.

	DOCUMENT TITLE: A Prospective, Post-Market, Multi-Center Study Evaluating ViBone in Cervical and Lumbar Spine Fusion	DOCUMENT NUMBER: CLP-0001
--	---	-------------------------------------

² Flexion/extension x-rays are not required at baseline, but will be collected if captured.

³ Flexion/extension x-rays are required at all follow-up visits.

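### Section 11.1 ties the Serious Adverse Reaction form and its seriousness-type criteria to communicable disease, while the safety outcome is unrestricted, so other serious ViBone reactions have no stated route into the incidence.

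*Combined protocol and SAP*

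**What the plan says.** The outcome is broad wherever it is named. The synopsis lists "Incidence of subjects experiencing ViBone-related serious adverse reactions" among the secondary outcomes. Section 10 gives "Incidence of ViBone-related serious adverse reactions" as its only safety evaluation, and Section 4.2 uses the same words. None of the three limits the type of reaction.

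Section 11.1 starts from an equally broad definition, taken from the regulation it cites: "a noxious and unintended response to any HCT/P for which there is a reasonable possibility that the HCT/P caused the response". It then turns to communicable disease. The sentence "Adverse reactions are further defined to include the following" leads to four criteria (fatal, life threatening, permanent impairment or damage, intervention including hospitalization), all under a stem that limits them to a communicable disease. The sentence that triggers the form reads, in part, "adverse reaction involving a communicable disease that is believed to be related to the use of ViBone occurs, a Serious Adverse Reaction form shall". The next sentence adds, for that same event, that "Aziyo must be notified within 24 hours of the Investigator becoming aware of the event".

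Three wider channels appear elsewhere:
- Table 1 has a row for "ViBone-Related Serious Adverse Reactions Assessment", marked as needed at follow-up and not restricted by type.
- Section 7.2.3 requires a surgical complication assessment at 6 and 12 months.
- The package insert (Appendix 4) obliges the physician to report promptly to the sponsor any adverse outcome that may be attributable to ViBone.

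**The concern.** The rule for completing the only study form named for serious reactions is narrower than the outcome. A site that follows 11.1 to the letter completes the form for a communicable-disease reaction. For any other serious graft reaction, 11.1 gives it neither a form to complete nor a test of seriousness.

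The statistics are descriptive (Section 12), so the count is itself the safety result. If its scope is unclear, two things can go wrong. A serious reaction may be missing from the numerator, or up to 20 centers may apply different rules, so that the pooled count has no single meaning. A low or zero figure could then be taken to cover every serious ViBone reaction when part of that range was never collected in a uniform way. Section 10 also says that its outcome measures will be compared with published or retrospective data; if that extends to safety, an unclear numerator weakens the comparison.

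**Working it through.** The documents give no expected reaction rate and no safety figure to reproduce. The check is therefore a comparison of texts, followed by a note on scale.

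**1. Scope of each element**

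| Element | Place | Limited to communicable disease? |
|---|---|---|
| Outcome | Synopsis, 4.2, 10 | No |
| Definition of adverse reaction | 11.1 | No |
| Four seriousness-type criteria | 11.1 | Yes, by the stem of the list |
| Serious Adverse Reaction form | 11.1 | Yes |
| 24-hour notice to the sponsor | 11.1 | Yes, tied to the same event as the form |
| 15-day FDA report | 11.1 | Yes, with the regulation cited as the reason |

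The cited regulation explains the limit on the FDA report. The protocol gives no reason for putting the same limit on the form while the outcome stays broad.

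**2. Do the wider channels close the gap?**

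- *Table 1 row.* It is unrestricted but gives no criterion for seriousness. Section 7.1 states: "Study assessments are summarized below in Table 1, and are further described in Section 7.2". No part of 7.2 describes this assessment.
- *Surgical complication assessment (7.2.3).* It has no seriousness or relatedness rule and no link to the outcome. It is also absent from Table 1.
- *Package insert.* Reporting is mandatory and broad, but there is no seriousness criterion, no study form and no link to the outcome.

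Each channel could bring a reaction to the sponsor's notice. None says whether that reaction is then counted. The two cross-reference gaps are clerical; they matter here only because 7.2 is where a site would look for the missing rule.

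**3. The product risks named in Section 6.2.1, tested against the 11.1 form trigger**

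- Transmission of disease: covered.
- Host-site infection: arguably covered, depending on how a site reads communicable disease.
- Lack of fusion: captured by the primary outcome.
- Inflammatory response: not covered unless a communicable disease is involved. If it led to reoperation or admission, it would fit the outcome's name and the quoted definition, yet meet no form trigger in 11.1.

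**4. Scale**

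Input: up to 50 subjects per cohort (synopsis, 6.1, 12.1), cohorts analysed separately (synopsis, 16.2), subjects as the unit (synopsis).

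- Step per subject = 100/n. At n = 50: 100/50 = 2.0 percentage points. If a cohort ended at an assumed 40 or 30: 100/40 = 2.5 or 100/30 = 3.3 points.
- Exact 95% upper limit for zero events = 1 − 0.025^(1/n). At n = 50: 1 − 0.025^(1/50) = 7.1%. With one event in 50 (2%), the exact interval is 0.05% to 10.6%.

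These figures show what one subject is worth in a small cohort. They would be the same with perfect capture, so they do not measure the defect.

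**The case against.** The strongest reply is that 11.1 is a reporting section built around the FDA rule for communicable-disease reactions. A narrow expedited-reporting rule can stand beside a broader study outcome without contradiction. The documents do not say that the incidence is counted from the 11.1 forms, and Table 1 gives the outcome its own unrestricted row. Nothing in 11.1 says the form is used only for communicable disease, and the list is introduced with a word that can be read as non-exhaustive. The four criteria are never labelled serious, and their explanatory text speaks of adverse events in general, so a site could apply them to any reaction. The case report forms, the reaction form and the sponsor's reporting procedure are not in the text and may settle the matter.

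Much of this stands. A reader might infer that non-communicable reactions will be left out, or that no rule requires them to be reported at all. The documents do not support either reading. The link from form to count is not written down, and the package insert requires prompt reporting of any adverse outcome that may be due to ViBone. Loss of events is possible, not shown.

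The reply does not remove the gap. If the incidence does not come from the 11.1 forms, the protocol does not say where it comes from. If the criteria may be read broadly or narrowly, centers may differ. A shared electronic form could prevent that, but the protocol as written does not establish that it does.

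**Conclusion.** The point holds as a mismatch of scope. The outcome and the quoted definition are unrestricted, whereas the form, the 24-hour notice and the seriousness-type criteria in 11.1 are limited to communicable disease. No other channel supplies a seriousness criterion or a route into the incidence. A serious non-communicable reaction could therefore be omitted or handled differently between centers.

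The size of any undercount cannot be derived, because no reaction rate is given and the counting rule is not stated. It would be wrong to conclude that the reported incidence will be too low by any particular amount. The conclusion rests on the written rules alone; forms and procedures outside the text could narrow the gap. It concerns one secondary outcome in a descriptive registry and leaves the primary fusion result untouched. It is worth correcting because that outcome is the study's only named safety measure and the correction is cheap.

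**What to change.** Reconcile 11.1 with Section 10 in one of two ways.

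(a) If all serious ViBone reactions are meant, require the Serious Adverse Reaction form, and apply the four listed criteria, for every ViBone-related reaction that meets the definition already quoted in 11.1. Keep the communicable-disease limit for the 15-day FDA report. State in Section 10 that the incidence is tabulated by cohort from these records, with communicable-disease reactions shown as a subset. Whether the 24-hour notice should also widen is for the sponsor to state; the outcome does not depend on it.

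(b) If only communicable-disease reactions are meant, relabel the outcome accordingly in the synopsis, 4.2, Section 10 and Table 1.

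Option (a) costs some wording and a few more forms, and the incidence may look less favourable. Option (b) costs wording only, but the study then makes no statement about other serious reactions to the graft. Neither needs an extra visit. The clerical gaps between Table 1 and Section 7.2 can be tidied in the same amendment, though the fix does not depend on them.
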